8.5 Methods for statistical analyses

Continuous variables will be presented with mean, median, 25th percentile, 75th percentile, standard deviation, minimum, maximum, and (if appropriate) the number of nonmissing observations. Categorical data will be displayed via absolute and relative frequencies for each category, including a category labeled as ‘missing’ when appropriate. The ‘missing’ category will not contribute to the denominators of relative frequencies.

All analyses will be done using values prior to rescue/intensification of treatment. Values collected after this time will be excluded from analyses. Sensitivity analyses may be conducted using all available data and including a time varying covariate that indicates rescue status.

The primary endpoint (EGP) will be tested for saxagliptin 5 mg/dapagliflozin 10 mg versus dapagliflozin 10 mg groups at the $\alpha=0.05$ level (2-sided). Other comparisons (contrasts) will be tested in an exploratory fashion at the $\alpha=0.05$ (2-sided) level. Therefore, no multiplicity control is required.

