4.2 Treatment Period

After the Randomization visit (Visit 3), patients will complete study visits at 1- to 4-week intervals according to the Study Plan (Table 1) until the end of the randomized treatment period (Visit 8, Week 16). During Weeks 6 to 16 of the double-blind treatment period of the trial, patients may be eligible for the addition of open-label rescue medication to their blinded treatment regimen in order to treat ongoing hyperglycemia, based upon established laboratory FPG values and repeat, confirmatory FPG criteria (Table 2).

Table 2 Criteria for Initiation of Rescue Therapy During the Randomized Treatment Period

Visit Period	Central Laboratory FPG
Week 6	FPG >270 mg/dL (15.0 mmol/L)
After Week 6 to Week 12 (excluding Week 12)	FPG >240 mg/dL (13.3 mmol/L)
After Week 12 to Week 16 (excluding Week 16)	FPG >200 mg/dL (11.1 mmol/L)

Abbreviation: FPG fasting plasma glucose.

Patients with a laboratory FPG value meeting the lack of glycemic control criterion at a pre-specified visit will be scheduled for a Follow-up Visit (within 3 to 5 days) to obtain a second laboratory FPG value and review the patient's glucose meter readings. If the repeat laboratory FPG value still meets the criterion, the patient must be rescued. Patients should continue receiving study medication while receiving rescue therapy. Patients who meet rescue criteria in the double-blind treatment period must first complete an OGTT and the Visit 8/End of Treatment procedures, including a glucose turnover study and DEXA scan, before receiving open-label rescue medication, to ensure that important trial endpoint measurements are collected. Rescued patients will be given open-label antidiabetic rescue medication in accordance with the approved product label in the applicable country at the discretion of the Investigator, in addition to their double-blinded study medication. Rescued patients will then continue in the double-blind treatment period according to their original visit schedule.

Following initiation of open-label rescue medication, rescued patients should have their glycemic response to the rescue medication evaluated by the Investigator. At the end of the study or at early termination, rescued patients should undergo a double tracer OGTT, glucose turnover study, and DEXA scan.

4.2.1 Treatment Period visits (Visits 4 to 7, Weeks 4, 8, 12, and 15)

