6.3 Recording of adverse events

6.3.1 Time period for collection of adverse events

AEs will be collected from time of signature of informed consent, during the Screening, Run-in, and Randomization periods, and throughout the treatment periods.

All AEs will be recorded on source documents.

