8.3 Definitions of analysis sets

Classification into Full analysis (FA), Per protocol (PP), and Safety sets will be conducted prior to the database lock.

Primary analyses of efficacy endpoints (primary and secondary) will be performed on the FA set. Supportive analyses will be carried out with the PP analysis set if more than 10% of patients from the FA set are excluded from the PP analysis set for important protocol deviations. All safety analyses will be based on the Safety set.

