8.3.1 Efficacy analysis set

Full analysis set

- The FA set will be defined as all randomized patients with a baseline and a post baseline efficacy assessment value. Patients will be analyzed according to the treatment assigned.

Per protocol analysis set

- The PP analysis set will be defined as all FA patients without an important protocol deviation that might affect the primary analyses. The criteria for important protocol deviations will be defined in the SAP. Patients will be analyzed according to the treatment received.

Safety analysis set

- The Safety analysis set will be defined as all randomized patients who received at least 1 dose of study medication. Patients will be analyzed according to the actual treatment received.

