8.5.5 Safety analyses

Descriptive statistics of demographic and other baseline characteristics will be calculated. Safety and tolerability will be assessed using standard tabulations of AEs and AEs of special interest (using predefined lists of preferred terms), laboratory values and marked abnormalities, vital signs, physical examinations, and ECGs. The number and percentage of patients with hypoglycemia will be tabulated and presented by treatment group.

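### Section 8.5 applies its pre-rescue cut-off to all analyses, so as written post-rescue laboratory, vital-sign and ECG values, and by inference adverse events, are left out of the safety summaries

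*Combined protocol and SAP*

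**What the plan says.** The opening text of section 8.5 sets the rule: "All analyses will be done using values prior to rescue/intensification of treatment. Values collected after this time will be excluded from analyses". It allows an optional sensitivity analysis on all available data with a time-varying rescue indicator, which section 8.5.4 repeats.

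Safety analyses are section 8.5.5, a subsection of 8.5: "Safety and tolerability will be assessed using standard tabulations of AEs and AEs of special interest". Laboratory values, vital signs, physical examinations and ECGs are also covered, together with counts and percentages of patients with hypoglycemia. No data window is given.

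On populations, section 8.3 says "All safety analyses will be based on the Safety set", and section 8.3.1 says "The Safety analysis set will be defined as all randomized patients who received at least 1 dose of study medication".

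On conduct, section 4.2 says "During Weeks 6 to 16 of the double-blind treatment period of the trial, patients may be eligible for the addition of open-label rescue medication". After that, "Patients should continue receiving study medication while receiving rescue therapy", and "Rescued patients will then continue in the double-blind treatment period according to their original visit schedule". Section 6.3.1 adds: "AEs will be collected from time of signature of informed consent, during the Screening, Run-in, and Randomization periods, and throughout the treatment periods". Note j to Table 1 has the Visit 8 procedures done before rescue and repeated at the end of treatment. Sections 5.3.1 and 6.3.8 call for summaries that cover every hypoglycemia event, with no rescue cut-off.

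**The concern.** The Safety set fixes which patients count. The sentence in 8.5 fixes which of their data count, and nothing in 8.5.5 overrides it. A programmer who follows the text would cut a rescued patient's safety record at rescue, although that patient is still taking blinded drug, now with an added antidiabetic agent.

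The safety objective (section 2.3) compares the combination with dapagliflozin and with placebo at Week 16. Two things are at stake:

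- **Lost on-drug information.** The repeat end-of-treatment laboratory, vital-sign and ECG results would be collected and then left out of the tables. This matters most for laboratory values and vital signs. Under the heading on adverse events based on examinations and tests, deterioration in a protocol-mandated value becomes an adverse event only if it meets a seriousness criterion or leads to stopping the drug (section 5.2 reads more broadly for laboratory results). The tables may therefore be the main place where such changes are seen.
- **Unequal follow-up.** Rescue is triggered by fasting plasma glucose, which the treatments affect. Observation time could then differ by arm, while the hypoglycemia table, for example, reports plain percentages.

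**Working it through.** The plan states no figure on this point, so there is none to reproduce. The check is one of scope first, then of size.

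**Scope**

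1. Does the rule reach safety? Its subject is all analyses. The paragraph before it in 8.5 gives general presentation rules for continuous and categorical data, which safety tables also need. Elsewhere the plan specifies efficacy when it means efficacy (8.3, 8.5.1), and 8.6 names efficacy and safety separately.
2. Which data does it reach? The word *values* fits laboratory, vital-sign and ECG results directly. An adverse event is not naturally a value, so its exclusion rests only on the phrase about all analyses and the missing exemption.
3. Does other text keep the data in? For hypoglycemia, yes: 5.3.1 and 6.3.8 ask for all events, so the plan contradicts itself. For the rest, 8.5.4 is optional and model-based, and the listing provision in 8.1 is not a comparison between arms.

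**Size**

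Inputs: 53 randomized patients (8.2); 16 weeks of treatment; rescue permitted from Week 6 (4.2). No rescue rate is given. Section 8.2 allows 10% in the two main arms for early termination, rescue and missing assessments together. Applied to all 53 (an assumption), this is 0.10 × 53 = 5.3, so 5 rescued is taken as the upper end and 1 as the lower.

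Planned exposure: 53 × 16 = 848 patient-weeks. Weeks lost per rescued patient = 16 − week of rescue. Share lost overall = rescued patients × weeks lost ÷ 848.

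| Rescue at | Weeks lost | Share of that patient's 16 weeks | 1 rescued | 5 rescued |
|---|---|---|---|---|
| Week 6 | 10 | 62.5% | 10/848 = 1.2% | 50/848 = 5.9% |
| Week 8 | 8 | 50% | 8/848 = 0.9% | 40/848 = 4.7% |
| Week 12 | 4 | 25% | 4/848 = 0.5% | 20/848 = 2.4% |

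The range is 0.5% to 5.9%.

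The early rows are outer limits. Take a trigger at Week 8 (Day 56). A confirmatory glucose follows 3 to 5 days later (4.2). If the turnover study is done that day, the OGTT comes 5 to 14 days after it (Table 1, note j). Rescue then starts between Day 56 + 3 + 5 = 64 and Day 56 + 5 + 14 = 75. That leaves 112 − 64 = 48 to 112 − 75 = 37 days, or 43% to 33% of the 112 days.

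**The case against.** The best reply is that the sponsor meant efficacy. The rule follows the list of outcome measures in 8.4, speaks of values, and comes just before a model-based sensitivity analysis and the significance level for the EGP endpoint. Where rescue is mentioned in 8.5.1, it concerns the primary analysis. This may well be the intent, and it weakens the claim for adverse events. The text still does not say so, and laboratory, vital-sign and ECG data remain caught by its wording.

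Several stronger readings are tempting but not supported:

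- *Serious events after rescue go missing.* They do not. Section 6.4 requires all serious adverse events to be reported, and 8.1 has all collected data listed.
- *Rescued patients lose their safety assessment.* They do not. Visit 8 procedures are completed before rescue, so one pre-rescue laboratory, ECG and examination record stays in.
- *Hypoglycemia after rescue is excluded.* Two sections say the opposite, so this is a conflict to resolve and not a clean exclusion.
- *One omitted serious event would change the safety conclusion.* Safety is descriptive, with no decision rule, so nothing in the plan supports this.
- *The loss is large, above all on placebo.* No rescue rate is given for any arm. The 10% allowance covers more than rescue, and section 1.2 says the HbA1c range was chosen with a low chance of rescue in mind.
- *The rule hides harm from the active drugs.* If rescue were most common on placebo, the cut would mainly remove placebo events, which would tend to make the active arms look relatively worse.

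**Conclusion.** The concern holds in a limited form. As written, 8.5 leaves post-rescue laboratory, vital-sign and ECG values out of the safety summaries, and adverse events by inference; for hypoglycemia it contradicts 5.3.1 and 6.3.8. The loss is from the between-arm summaries, not from safety reporting or oversight.

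The amount is about 0.5% to 5.9% of patient-weeks. This rests on the assumptions that 1 to 5 of 53 patients are rescued and that rescue begins between Week 6 and Week 12; later rescue would give less. The overall share is small, but it falls entirely on patients taking blinded drug plus rescue medication. It may differ by arm, though the documents do not allow the direction or size of any imbalance to be stated. The primary result and the sample size are not affected.

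**What to change.** 1. In section 8.5, insert the word *efficacy* before *analyses* in both sentences of the rule. The primary analysis does not change, because 8.5.1 already leaves out rescued patients.
2. In section 8.5.5, state that safety summaries use all data from first dose to Week 16 regardless of rescue. This also removes the conflict with 5.3.1 and 6.3.8. Blood pressure is both an outcome in 8.4 and a safety variable, so it is worth saying that the cut-off applies only to the first use.
3. Optionally, add a supplementary tabulation limited to the pre-rescue period, so that events possibly due to the rescue drug can be told apart.

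The cost is one inserted word in each of two sentences and a short addition to 8.5.5, plus one extra set of tables if item 3 is taken up. The data are already collected; no visit, assessment or sample-size change is needed.

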8.5.1 Analysis of the primary variable

The primary efficacy analysis will be performed using an analysis of covariance (ANCOVA) method for the change from baseline at Week 16, with terms for treatment group, baseline HbA1c subgroup ($\leq 8.5\%$ versus $> 8.5\%$), baseline treatment (metformin versus metformin/sulfonylurea) and baseline value in the model. Point estimates and 95% confidence intervals will be calculated for the adjusted mean changes within each treatment group as well as for the differences in adjusted mean changes between treatment groups. A subject who early terminates, is rescued, or does not have a Week 16 assessment for any other reason will not contribute to the primary analysis.

All inferential procedures of the secondary efficacy endpoints will be done at a 5% level of significance (2-sided).

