Approximately 53 patients with Type 2 diabetes mellitus (T2DM) with inadequate glycemic control receiving metformin at a dose of ≥ 1000 mg/day for at least 8 weeks prior to screening, will be randomized to 1 of 3 treatment groups.

Duration of treatment

Study duration will be at least 18 weeks, including a 1-week screening period, a 1-week run-in period, and a 16-week double-blind treatment period.

Investigational product, dosage, and mode of administration

Saxagliptin and matching placebo:

Saxagliptin 5 mg tablets or placebo matching saxagliptin will be administered orally QD for the 16-week double-blind treatment period.

Dapagliflozin and matching placebo:

Dapagliflozin 10 mg tablets or placebo matching dapagliflozin will be administered orally QD for the 16-week double-blind treatment period.

Other treatments

Metformin and Sulfonylurea (glipizide, glyburide, glimepiride)

Up to Visit 8 (Week 16), patients should continue to administer the same type and dose of metformin therapy they were using at study entry. Metformin and sulfonylurea will not be provided in pre-packaged kits by the Sponsor and will be sourced locally by the site and in accordance with the approved package labeling. Metformin and sulfonylurea should be administered and stored according to product and country-specific labelling.

Rescue therapy:

Patients who require rescue therapy should receive standard of care treatment; however, Bydureon 2 mg subcutaneously is highly suggested.

Statistical methods

Sample size estimate:

The primary comparison will be comparing EGP for saxagliptin 5 mg plus dapagliflozin 10 mg versus dapagliflozin 10 mg at Week 15.

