With 19 patients per treatment group, there will be 90% power to detect a difference in mean EGP of 0.39 mg/kg/min between saxagliptin 5 mg plus dapagliflozin 10 mg and dapagliflozin 10 mg groups assuming a standard deviation of 0.32 using a 2 group t-test with a 0.050 2-sided significance level. Assuming that 10% of subjects in the primary comparison arms early terminate, are rescued, or do not have a Week 16 assessment for any other reason, a total of 21 subjects per treatment arm need to be randomized for each of the saxagliptin 5 mg plus dapagliflozin 10 mg and dapagliflozin 10 mg treatment arms. Approximately 11 subjects will be randomized to the placebo treatment arm for exploratory comparisons of saxagliptin 5 mg plus dapagliflozin 10 mg to placebo (approximately 80% power), for a total of approximately 53 subjects randomized.

Assuming that 70% of screened subjects will fail to meet screening criteria, a total of 177 subjects will need to be screened.

Statistical considerations

Analysis populations:

Classification into Full analysis (FA), Per protocol (PP), and Safety analysis sets will be conducted prior to the database lock.

Primary analyses of efficacy endpoints (primary and secondary) will be performed on the FA set. Supportive analyses will be carried out with the PP analysis set if more than 10% of patients from the FA set are excluded from the PP analysis set for important protocol deviations. All safety analyses will be based on the Safety analysis set.

Efficacy analysis set

Full analysis set

The FA set will be defined as all randomized patients with a baseline and a post baseline efficacy assessment value. Patients will be analyzed according to the treatment assigned.

Per protocol analysis set

The PP analysis set will be defined as all FA patients without an important protocol deviation that might affect the primary analyses. The criteria for important protocol deviations will be defined in the statistical analysis plan. Patients will be analyzed according to the treatment randomized/received.

Safety analysis set

The Safety analysis set will be defined as all randomized patients who received at least 1 dose of study medication. Patients will be analyzed according to the actual treatment randomized/received.

Analysis of the primary variable:

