The primary endpoint (EGP) will be tested in a confirmatory fashion for saxagliptin 5 mg plus dapagliflozin 10 mg versus dapagliflozin 10 mg at the $\alpha=0.05$ (2-sided) level. The other comparisons (contrasts) will be tested in an exploratory sense at the $\alpha=0.05$ (2-sided) level. No multiplicity control is required.

The primary efficacy analysis will be performed using an analysis of covariance (ANCOVA) method for the change from baseline at Week 16, with terms for treatment group and baseline HbA1c subgroup ($\leq 8.5\%$ versus $> 8.5\%$), and baseline EGP value in the model. Point estimates and 95% confidence intervals will be calculated for the adjusted mean changes within each treatment group as well as for the differences in adjusted mean changes between treatment groups. A subject who terminates from the study early, is rescued, or does not have a Week 16 assessment for any other reason will not contribute to the primary analysis.

TABLE OF CONTENTS	PAGE
PROTOCOL SYNOPSIS.....	3
TABLE OF CONTENTS.....	11
LIST OF ABBREVIATIONS AND DEFINITION OF TERMS	16
1. INTRODUCTION	19
1.1 Background and rationale for conducting this study	19
1.2 Rationale for study design, doses and control groups.....	20
1.3 Benefit/risk and ethical assessment.....	24
1.3.1 Ethical safety considerations.....	24
1.3.2 Saxagliptin	25
1.3.3 Dapagliflozin.....	25
1.3.4 Potential benefits to patients	26
1.4 Study Design	26
2. STUDY OBJECTIVES.....	29
2.1 Primary objective	29
2.2 Secondary objectives	29
2.3 Safety objectives	32
2.4 Exploratory objectives	32
3. SUBJECT SELECTION, ENROLLMENT, RANDOMISATION, RESTRICTIONS, DISCONTINUATION AND WITHDRAWAL.....	33
3.1 Inclusion criteria	33
3.2 Exclusion criteria	34
3.3 Subject enrollment and randomization	36
3.3.1 Procedures for randomization.....	37
3.4 Procedures for handling incorrectly enrolled or randomized subjects.....	37
3.5 Methods for assigning treatment groups.....	38
3.6 Methods for ensuring blinding.....	38
3.7 Methods for unblinding.....	38
3.8 Restrictions	39
3.9 Discontinuation of investigational product	39
3.9.1 Discontinuation guidelines for protocol-defined major hypoglycemia episodes or recurrent non-major hypoglycemia episodes.....	40
3.9.2 Procedures for discontinuation of a subject from investigational product	40

3.10	Criteria for withdrawal.....	41
3.10.1	Screen failures.....	41
3.10.2	Withdrawal of the informed consent.....	42
3.11	Discontinuation of the study	42

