2. STUDY OBJECTIVES

2.1 Primary objective

Primary Objective:	Outcome Measure:
To compare the post-IP minus pre-IP endogenous glucose production (EGP) during the glucose turnover study in saxagliptin 5 mg plus dapagliflozin 10 mg vs dapagliflozin at Week 15.	
 Post-IP minus pre-IP EGP (mg/kg/min) during the glucose turnover study at Week 15.

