8.4 Outcome measures for analyses

The mean values will be compared between the treatment groups for the following measures:

1. Post-IP minus pre-IP EGP during glucose turnover study at Week 15.
2. Post-IP minus pre-IP EGP during glucose turnover study at Week 0 and the change from Week 0 to Week 15.
3. Pre-IP EGP during glucose turnover study at Week 15 and the change from Week 0 to Week 15.

4. Pre-glucose load EGP during the OGTT at Week 16 and the change from Week -1 to Week 16.
5. Change from Week -1 to Week 16 in post-glucose load EGP during the OGTT.
6. Change from Week -1 to Week 16 in Rd and Ra during OGTT.
7. Change from Week 0 to Week 16 in HbA1c.
8. Change from Week 0 to Week 15 in pre-IP plasma glucose during glucose turnover study.
9. Change from Week -1 to Week 16 in pre-glucose load FPG and post-glucose load PPG during the glucose turnover study.
10. Change from Week -1/0 to Week 15/16 in fasting plasma glucagon, C-peptide, and insulin during the glucose turnover study and OGTT.
11. Change from Week -1/0 to Week 15/16 in plasma glucagon, C-peptide, and insulin during the glucose turnover study and OGTT.
12. Change from Week 0 to Week 15 in post-IP minus pre-IP plasma glucagon, C-peptide, and insulin during the glucose turnover study.
13. Change from Week -1 to Week 16 in insulin secretion, beta cell function, and insulin sensitivity during OGTT.
14. Change in glucose oxidation and lipid oxidation during the baseline of the glucose turnover study, during the baseline of the OGTT, and post-glucose load during the OGTT.
15. Change in plasma ketones during the baseline of the glucose turnover study and OGTT.
16. Change from Week 0 to Week 15 in pre-IP, post-IP, and post-IP minus pre-IP in counterregulatory hormones during glucose turnover study.
17. Change from Week -2 to Week 16 in body weight and BMI; and percent body fat and fat distribution calculated from the DEXA scans.
18. Change from Week -1 to Week 16 in plasma GLP-1, GIP, and FFA during OGTT.
19. Change from Week -2 to Week 16 in FFA.
20. Change from Week 0 to Week 16 in waist to hip ratio, BP, and lipids.

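### The confirmatory ANCOVA models change from baseline at Week 16, but the primary endpoint is the Week 15 post-dose minus pre-dose EGP difference, and the exclusion rule discards valid Week 15 values

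*Combined protocol and SAP*

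**What the plan says.** **Endpoint.** Section 2.1 gives the primary objective as "To compare the post-IP minus pre-IP endogenous glucose production (EGP) during the glucose turnover study", combination against dapagliflozin, at Week 15. Section 8.4, item 1, lists "Post-IP minus pre-IP EGP during glucose turnover study at Week 15". The synopsis sample-size text agrees on timing: "The primary comparison will be comparing EGP for saxagliptin 5 mg plus dapagliflozin 10 mg versus dapagliflozin 10 mg at Week 15".

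**Analysis.** Section 8.5.1 states: "The primary efficacy analysis will be performed using an analysis of covariance (ANCOVA) method for the change from baseline at Week 16". The synopsis model is also an "analysis of covariance (ANCOVA) method for the change from baseline at Week 16". Section 8.2 likewise frames the primary endpoint as a change in EGP relative to baseline, evaluated at Week 16. The 8.5.1 covariates are HbA1c stratum, background therapy and baseline value. The synopsis has HbA1c stratum "and baseline EGP value in the model", without background therapy.

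**Secondary endpoints close to that wording.** Section 8.4, item 2, is "Post-IP minus pre-IP EGP during glucose turnover study at Week 0 and the change from Week 0 to Week 15". Items 4 and 5 cover EGP from the OGTT, including Week 16.

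**Schedule.** Table 1 and Section 5.1.8 place turnover studies at Visit 3 (Week 0) and Visit 7 (Week 15, Day 103). Visit 8 (Week 16, Day 112) has the double tracer OGTT.

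**Exclusion.** Section 8.5.1 and the synopsis remove from the primary analysis anyone who terminates early, is rescued or lacks a Week 16 assessment. The 10% attrition allowance in Section 8.2 and the synopsis uses the same condition, counting patients who "do not have a Week 16 assessment for any other reason". Section 8.5, by contrast, keeps values obtained before rescue and discards only later ones.

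**The concern.** There is one confirmatory test, and the text describing it does not fix its dependent variable. Read literally, it names a visit at which the primary variable is not scheduled and a change score that resembles endpoints listed as secondary. Two analysts could follow the plan and test different quantities.

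The exclusion rule is a second problem. It removes a primary measurement already taken because of something that happens afterwards. One such event is rescue, which depends on glycemic control, so the removal need not be neutral between arms. It also conflicts with the rule in Section 8.5 on pre-rescue values.

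**Working it through.** **1. The plan's own figure.** Inputs from Section 8.2: difference 0.39, SD 0.32, two-sided 0.05, two-group t-test, 19 per arm, 90% power. The noncentrality is 0.39 / (0.32 × √(2/19)) = 3.76 on 36 degrees of freedom, which gives power of 95.5%. Power of 90% needs 16 per arm (91.5%; 15 gives 89.6%). The stated 90% at 19 is therefore not reproduced. The error is conservative and separate from this point; 19 per arm is used below.

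**2. What 'change from baseline' could mean.** Write D15 for Week 15 post-dose minus pre-dose EGP, Pre15 and Post15 for its parts, and B for Week 0 pre-dose EGP. Under Section 8.1, baseline precedes the first dose, so B is the default. The model has treatment, both strata and B.

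- *Outcome D15, or D15 − B.* Subtracting B lowers the coefficient of B by 1 and leaves the residuals unchanged. The treatment estimate, SE and p-value are identical; 2,000 simulated data sets agreed to rounding error. Only the within-arm adjusted means differ.
- *Outcome Post15 − B (a single EGP level).* Since Post15 = D15 + Pre15, the treatment coefficient equals that for D15 plus that for Pre15. Pre15 follows 15 weeks of treatment and is itself a secondary endpoint (Section 8.4, item 3). The documents give no arm difference for it, so these values are assumed:

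| Assumed arm difference in Pre15 | −0.2 | −0.1 | 0 | +0.1 | +0.2 |
|---|---|---|---|---|---|
| Contrast tested (0.39 + difference) | 0.19 | 0.29 | 0.39 | 0.49 | 0.59 |

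- *Outcome: Week 0 to Week 15 change in the post-minus-pre difference (item 2).* The expected contrast is 0.39 − d0, where d0 is the Week 0 arm difference in that quantity. For assumed d0 of 0, 0.195 and 0.39 it is 0.39, 0.195 and 0.
- *Outcome: Week 16 OGTT EGP.* This contains no post-dose minus pre-dose difference, and the documents give no basis for a figure.

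**3. A conditional warning on the covariate.** Week 0 post-minus-pre EGP is not a baseline under Section 8.1, because the first randomized dose is taken at Time 0 of that study (Table 3, footnote c). If it were used as the covariate anyway, the expected adjusted difference would be 0.39 − ρ × d0. Assume ρ of 0.3, 0.5 or 0.7 and SD 0.32 at both weeks (100,000 simulated trials each):

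| Assumed d0 | Adjusted difference | Power at 19 per arm |
|---|---|---|
| 0 | 0.39 / 0.39 / 0.39 | 96.4 / 98.6 / 99.9% |
| 0.195 | 0.33 / 0.29 / 0.25 | 86.3 / 84.6 / 87.6% |
| 0.39 | 0.27 / 0.195 / 0.12 | 61.3 / 42.6 / 25.3% |

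This is a reason to name the covariate, not the expected effect of the plan.

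**4. Exclusion: can the case arise?** By visit label, Visit 7 is the only scheduled fasting glucose visit in the last rescue band of Table 2 (after Week 12, before Week 16). The repeat test comes 3 to 5 days later, nominally Days 106 to 108. That is after the Visit 7 turnover study and before Day 112. A patient who then meets the rescue rule has a pre-rescue Week 15 value that Section 8.5.1 removes.

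**5. Exclusion: how many?** The Visit 7 to Visit 8 gap is 112 − 103 = 9 days. With the Table 1 windows it runs from (112 − 4) − (103 + 5) = 0 to (112 + 4) − (103 − 5) = 18 days. Assume the planned 10% loss accrues at a constant rate over 112 days:

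- 9-day gap: 21 × (0.9^(103/112) − 0.9) = 0.16 patients per arm
- 18-day gap: 21 × (0.9^(94/112) − 0.9) = 0.32 patients per arm

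Rescue triggered by the Visit 7 glucose could add to this. Losing 0, 1 or 2 per arm from 19 gives power of 95.5, 94.4 or 93.1%.

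**The case against.** The objectives and Section 8.4 fix the endpoint clearly, and 8.5.1 need only supply the method. 'Week 16' may be a leftover: the table of contents still calls Visits 7 and 8 Weeks 16a and 16b. Section 1.2 calls the primary endpoint a change in EGP, which may mean the within-test difference. On that reading the test is unaffected, and 'Week 16 assessment' in the exclusion sentence carries the same leftover label. The post-dose level alone is not a listed outcome, and the ranges above rest on assumed values.

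This is a fair account of probable intent, and the size of the damaging readings is indeed unknown. But the body text now separates Weeks 15 and 16, and nothing maps one to the other. Correcting the label would still leave open which change and which baseline are meant.

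On exclusion, Sections 4.2 and 7.7.2 require the Visit 8 procedures and a turnover study before rescue medication starts. A patient caught at Visit 7 would therefore probably have a Week 16 assessment. That stands, and it limits the missing-visit route. It does not help with the words removing anyone who is rescued or terminates early, which apply whatever was measured first. It can also be said that Section 8.5 governs values and 8.5.1 governs patients. Applied together, though, they still discard a value that 8.5 would keep.

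**Conclusion.** The concern holds. The confirmatory model as written does not analyse the stated primary endpoint, and the exclusion rule removes valid Week 15 data. The case rests on what is being estimated, not on power. If the outcome is the Week 15 difference and the covariate is Week 0 pre-dose EGP, the test is unchanged. If the outcome is anything else, the contrast is a different quantity, by an amount the documents do not determine. The expected loss from the exclusion is a fraction of a patient per arm under even attrition, and two lost per arm would still leave 93.1% power. The point must nevertheless be fixed, because a single confirmatory test needs one dependent variable settled before unblinding.

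**What to change.** - **Section 8.5.1 and synopsis, model.** Define the primary analysis as an ANCOVA of Week 15 post-dose minus pre-dose EGP from the Visit 7 turnover study, with treatment, HbA1c stratum, background-therapy stratum (missing from the synopsis) and Week 0 pre-dose EGP. State that the Week 0 post-minus-pre difference is not the covariate, because it is measured after the first randomized dose.
- **Section 8.5.1 and synopsis, exclusion.** Replace the whole sentence with: *A patient is left out only if there is no Week 15 (Visit 7) glucose turnover study obtained before rescue or early termination. Later rescue, later termination or a missed Visit 8 does not remove a valid Week 15 value.* Add that the scheduled Visit 7 study counts if a later pre-rescue study also exists. Turnover studies done at an earlier rescue or termination are not Week 15 values and stay outside this analysis.
- **Section 8.2 and synopsis, sample size.** State the same Week 15 endpoint in Section 8.2, and reword the attrition clause in both places to refer to the Visit 7 study.
- **Unchanged.** Keep Week 16 OGTT EGP and the Week 0 to Week 15 change as secondary endpoints.

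The cost is protocol and SAP wording only, with no new data or patients.
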